11.10. Appendix 10: Protocol for Acetylcholinesterase (ACHE) assay

V0.4

Checklist (before starting experiment)

- ☐ Biotek Synergy H1m is free to use. Start a new experiment with existing protocol and chose the AchE protocol. Adjust the plate layout according to today's experiment
- ☐ Plate layout for today is set up (on paper or in PipettePilot)
- ☐ Work bench is tidy, washing buffer reservoir cleaned, pipettes working properly
- ☐ Lab timer is ready
- ☐ Necessary buffers and chemicals are available

Important things to remember

- ☐ Work quickly but carefully! Avoid delays! Try not to exceed intervals by more than 5 min.
- ☐ Mix all reagents gently and avoid foaming! Do not heat reagents to quicken thawing!
- ☐ Use gloves and change them regularly! Because of high sample dilutions any contamination will have critical impact on the result!
- ☐ Reconstitute DTNB (Ellman's reagent) and ATCh-iodide (Acetylthiocholine-iodide) in assay buffer and prepare dilution series of recombinant AchE standard **when ready to start the assay right away!** Have samples ready before preparing the standard series!
- ☐ Briefly spin or centrifuge vial of recombinant AchE standard before opening
- ☐ Use electronic pipettes (be familiar with working principle)
- ☐ Use the pipette that is best suited for the desired volume: blue tips: above 200µl; green tips: 20-300µl; yellow tips: 10-200µl; and red tips: below 10µl.

Date: ____ / ____ / ____	PlateNr. _____	Operator(s): _____
_____	_____	_____
_____	_____	_____

Please note lot nr for every reagent used in today's assay:

Item	Supplier	PartNr	LotNr
Clear 96 non-binding plate	greiner	655101	
rec. AchE standard	abcam	ab138871	
		Reconstituted on:	
DTNB	Merck/Sigma	A14331.03	
ATCh-iodide	Merck/Sigma	A5751-1G	
Sample diluent			Preparation date:
a. 0.9% normal saline (NaCl)	Self-made	N/A	__ . __ . ____

b. assay buffer (see below)			__ . __ . ____
Assay buffer			Preparation date:
50mM TRIS-HCl pH 8.2	Self-made	N/A	__ . __ . ____
PBS pH 7.2	ThermoFisher	28372	
Phenserine tartrate	Kragerø Tablett	N/A	

Please check chapter on preanalytical sample handling before starting an assay!

Reagent preparation

TRIS-HCl (0.05M pH 8.2): *2-Amino-2-hydroxymethyl-propane-1,3-diol (MW 121,14)*

Weigh in 6.06g TRIS and dissolve in 950ml ddH₂O

Adjust pH with 1N HCl to 8.2 (tolerance ± 0.1)

Fill up to 1000ml with ddH₂O

Store at RT

Perform the following preparations while samples are thawing on ice

DTNB: *5,5'-Dithio-bis(2-nitrobenzoic acid) [CAS 69-78-3], MW = 396.35;*

10mM = 3.9635mg/ml.

Weigh in about 4-5mg (a bit less than a peppercorn size) per plate. Dissolve in assay buffer to achieve a 10mM working solution. You will need at least 800µl of this per plate. You can use a 2ml Sarstedt screw cap tube for this.

☐ weighed in: ____ mg \rightarrow dissolve in $x/3.9635 =$ ____ ml assay buffer
(fx1)

NB! If not readily dissolved, heat to 37°C. This is usually not necessary.

ATCh: *(2-Mercaptoethyl)trimethylammonium iodide acetate [CAS 1866-15-5], MW = 289.18;*

15mM = 4.3377mg/ml.

Weigh in about 10mg (peppercorn size) per plate. Dissolve in assay buffer to achieve a 15mM working solution. You will need at least 2.4ml of this per plate. You can use a 2ml Sarstedt screw cap tube for this. However, first add only half of the required buffer (gaining a 30mM solution) and then combine it with the same volume of assay buffer in a 15ml tube to achieve the final 15mM.

☐ weighed in: ____ mg \rightarrow dissolve in $x/(2*4.3377) =$ ____ ml assay buffer
(fx2)

☐ combine ____ ml of 30mM solution (fx2) with ____ ml assay buffer to achieve 15mM

[figure not shown]
Phenserine tartrate: (MW 487.5); **10mM = 4.875mg/ml.**

Weigh in about 1mg per plate. Dissolve in assay buffer to achieve a 10mM working solution. You can use a 2ml Sarstedt screw cap tube for this. The 10mM phenserine tartrate stock is diluted 1:200 to achieve a 50nM working concentration.

- ☐ weighed in: ____ mg \rightarrow dissolve in $x/4.875 =$ ____ ml assay buffer
($\times 3$)
- ☐ prepare a 1:200 dilution in assay buffer, e.g. add 100 μ l 10mM stock + 8.9ml assay buffer

AchE standard: Component D of the ab138871 abcam AchE activity assay (colorimetric)
Component D has been reconstituted in 0.1% BSA (50 U/ml) and was frozen in 10 μ l portions.

Make a serial dilution as described below in sample buffer.

NB! Diluted AchE standard is stable for about 4 hours!

Sample preparation

- ☐ Thaw samples on ice
- ☐ **Serum** (AchE) and **plasma** (BchE) are to be diluted **1:50** to **1:100** in assay buffer
- ☐ **Whole blood** samples are to be diluted **1:100** in assay buffer
- ☐ Normal saline stabilized whole blood has a 1:100 dilution
(99 vol normal saline + 1 vol whole blood)
- ☐ Run samples in triplicates or more replicates

Recommendation: 1:50 \rightarrow Add 5 μ l sample to 245 μ l assay buffer (enough for 20 replicates)

1:100 \rightarrow Add 5 μ l sample to 495 μ l assay buffer

Include at least 4 wells with buffer instead of sample as blank

Include same sample type QC control on plate. QC measurements must be logged in ACHE CONTROL TRACKING SHEET over time.

Phenserine treatment (50nM) of samples should result in an activity decrease to 20-40% of normal levels.

Plate layout

	1	2	3	4	5	6	7	8	9	10	11	12
A	BL	BL	BL	QC	QC	QC	QC					
B	BL	BL	BL	QC	QC	QC	QC					
C	BL	BL	BL	SPL1 1:100	SPL1 1:100	SPL1 1:100	SPL1 1:100					
D	31.2	31.2	31.2	SPL1 1:100	SPL1 1:100	SPL1 1:100	SPL1 1:100					
E	62.5	62.5	62.5	SPL2 1:100	SPL2 1:100	SPL2 1:100	SPL2 1:100					
F	125	125	125	SPL2 1:100	SPL2 1:100	SPL2 1:100	SPL2 1:100					
G	250	250	250	QC	QC	QC	QC					
H	500	500	500	QC	QC	QC	QC					

1-3 = AchE standard, **X** = Assay buffer with 50nM phenserine tartrate;

QC = “Blood 2” for whole blood AchE; = “Serum 2” for serum AchE;

Plate ID: _____

Assay procedure

☐ Confirm that samples and reagents have been prepared, Synergy H1m is pre-heated to 37C

1) *Make assay working solution (example is for one whole 96well plate) by mixing*

☐ 750µl of 10mM DTNB in assay buffer with

☐ 33ml assay buffer

→ final concentration will be 0.2mM (in the 300µl assay volume)

2) *Make 50nM phenserine tartrate assay working solution (example is for 16 wells) by mixing*

☐ 150µl of 10mM DTNB in assay buffer with

☐ 6.6ml assay buffer with 50nM phenserine

3) *Fill each well of the 96well plate with assay working solution*

☐ 270 µl assay working solution w or w/o phenserine tartrate according to plate layout

4) *Add sample(s) to each well*

☐ 10µl sample, standard, or assay buffer (blank) per well

5) *Load plate to Synergy H1m*

☐ Start read procedure. The reader will mix the plate, perform a pre-substrate read and start incubation of the plate. You will be prompted to continue the read. Wait until 10mins have passed (see next step).

☐ Incubate for 10mins inside the plate reader

6) *Add ATCh (substrate)*

NB! The reactions will start at soon as the substrate is added. Avoid longer delays between first and last well

☐ Add 20µl 15mM ATCh solution to each well with multichannel electronic pipette.

Change tips between columns

→ final concentration will be 1mM

The solution will turn pale yellow upon addition of the substrate

7) *Continue read protocol*

☐ Place plate back to the Synergy H1m reader and continue run by acknowledging the prompt on the screen and clicking on “RUN” (green circle with play symbol) and then choosing “Resume read”

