To evaluate compliance, the study will measure the extent to which participants take the study medication according to the protocol. Compliance will be assessed using the subject diary and the registration of returned capsules.

Exploratory Objectives:

To evaluate changes in specific biomarkers of Alzheimer's Disease (AD) in cerebrospinal fluid (CSF): A β 1-40, A β 1-42, Tau, and p-tau, and in blood plasma: p-tau217 and NfL.

To assess phenserine's potential short-term effects on specific cognitive tests using the FLAME Memory Composite and other cognitive sub-tests.

To evaluate changes in overall cognitive function using the Montreal Cognitive Assessment (MoCA):

Primary Endpoint:

Changes in exosome biomarkers of pre-programmed cell death, synaptic integrity and function, neuroinflammation, and AD-related protein trafficking in participants treated with phenserine versus those treated with donepezil. Although patients and site staff will be unblinded to the treatment modality administered, they will be blinded to the results of the biomarker evaluations until the study is completed.

Key Secondary Endpoints:

Safety and tolerability of phenserine compared to donepezil in participants with early or mild AD based on the frequencies of reported or observed adverse events (AEs) and serious adverse events (SAE), vital signs, clinical laboratory evaluations, ECGs, and modified CSSRS scores.

Other Secondary Endpoints:

Pharmacokinetic parameters will be assessed at steady state for determination of dose-response relationships for phenserine and donepezil.

Evaluate the proportion of participants in the phenserine arm who achieve the target AChE inhibition of approximately 45%, stratified by dose regime and assess the time required to reach the target AChE inhibition of ~45% and the duration participants maintain this inhibition during the treatment period. Blood samples will be analyzed for Acetylcholinesterase (AChE) activity using a modified Micro-Ellman method (22) normalized to recombinant AChE enzyme activity (refer to Appendix 10).

Compliance will be recorded, based on drug count and subject diary, including the proportion of participants complying with the treatment schedule. Compliance is defined as drug intake within 80-120% of the scheduled dosing.

Exploratory Endpoints:

Assess changes in Alzheimer's Disease (AD) biomarkers in cerebrospinal fluid (CSF): A β 1-40, A β 1-42, Tau, and p-tau, and in blood plasma: p-tau217 and NfL.

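### Appendix 10's recipe for the 50 nM phenserine assay control yields 50 µM by its stated ratio and 111 µM by its worked example; the error is confined to that control

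*Protocol*

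**What the plan says.** Protocol Section 3 (Other Secondary Endpoints) names the assay: "Blood samples will be analyzed for Acetylcholinesterase (AChE) activity using a modified Micro-Ellman method (22) normalized to recombinant AChE enzyme activity". It refers to Appendix 10 (Section 11.10) for the method.

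In that appendix the phenserine tartrate stock is defined by "10mM = 4.875mg/ml" at a molecular weight of 487.5. The dilution instruction reads "The 10mM phenserine tartrate stock is diluted 1:200 to achieve a 50nM working concentration". The checklist line beneath it gives an example: "prepare a 1:200 dilution in assay buffer, e.g. add 100" µl of "10mM stock + 8.9ml assay buffer".

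Step 2 of the assay procedure takes the result as ready to use. It mixes 150 µl of 10 mM DTNB with "6.6ml assay buffer with 50nM phenserine". Step 3 fills each well with 270 µl of "assay working solution w or w/o phenserine tartrate according to plate layout", and the later additions bring the well to 300 µl. The expected reading is stated under sample preparation: "Phenserine treatment (50nM) of samples should result in an activity decrease to 20-40% of normal levels".

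The assay feeds three secondary outcomes in SAP Sections 4.5 and 8.3: the proportion reaching about 45% inhibition, the time to reach it and the time spent above it. SAP Section 8.3 summarises all three descriptively and graphically.

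**The concern.** The appendix is an operative bench instruction. A technician who follows it exactly cannot make the reagent it names, and the stated ratio and the worked volumes do not agree with each other.

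The spiked wells are the part of the plate where a known inhibitor should produce a known partial loss of activity. The blanks, the recombinant standards and the 'Blood 2'/'Serum 2' samples are described without any inhibitor. If the spiked wells are almost fully inhibited, they show that phenserine blocks the enzyme. They say nothing about how the assay behaves at intermediate inhibition, which is where the 45% target lies.

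**Working it through.** **Inputs, all from Appendix 10.** Stock 4.875 mg/ml, molecular weight 487.5; stated ratio 1:200; stated result 50 nM; example 100 µl stock plus 8.9 ml buffer; working solution 6.6 ml phenserine buffer plus 0.15 ml DTNB; 270 µl of working solution in a 300 µl well; expected residual activity 20-40% at 50 nM.

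**1. Is the stock labelled correctly?** 4.875 / 487.5 = 0.010 mol/l = 10 mM. Yes.

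**2. Stated ratio.** Final concentration = stock / dilution factor.
- One part in 200: 10 mM / 200 = 50 µM.
- One part plus 200 parts: 10 mM / 201 = 49.75 µM.
- Stated: 50 nM. Neither reading reproduces it; 50 µM / 50 nM = 1,000.
- Factor needed for 50 nM: 10 mM / 50 nM = 200,000.

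**3. Worked example.** Total volume = 0.1 + 8.9 = 9.0 ml. Factor = 9.0 / 0.1 = 90. Concentration = 10 mM / 90 = 111.1 µM, which is 111.1 µM / 50 nM = 2,222 times the stated value and 2.2 times a true 1:200. A true 1:200 of 100 µl needs 0.1 × 200 − 0.1 = 19.9 ml of buffer.

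**4. Is there a later dilution that rescues it?** No intermediate step is written. The 9.0 ml made by the example would directly supply the 6.6 ml used in step 2. Step 2 and the well fill together give 6.6/6.75 × 270/300 = 0.88. In the well this is 44 nM if the buffer really is 50 nM, 44 µM if the 1:200 ratio is followed, and 97.8 µM if the example is followed.

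**5. Is the rest of the appendix reliable?** Yes, where checked. DTNB in the well: 10 mM × 0.75/33.75 × 270/300 = 0.2 mM, as stated. Substrate in the well: 15 mM × 20/300 = 1 mM, as stated. The 1:50 and 1:100 sample dilutions also reproduce (250/5 and 500/5). The phenserine step is an isolated error.

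**6. Effect on the 20-40% expectation (assumption).** The documents give no half-inhibition concentration. Take residual activity = 1 / (1 + (C/IC50)^h), zero at full inhibition, and calibrate it to the appendix's statement that 50 nM leaves a residual r of 0.2 to 0.4. Then IC50 = 50 nM × (r/(1−r))^(1/h). The factor of 0.88 applies to every prepared strength alike, so it cancels.

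| Hill slope h | IC50 (nM) | Residual at 50 µM | Residual at 111 µM |
|---|---|---|---|
| 1 | 12.5 to 33.3 | 0.02% to 0.07% | 0.01% to 0.03% |
| 0.5 | 3.1 to 22.2 | 0.8% to 2.1% | 0.5% to 1.4% |

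Every value is far below 20%.

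**The case against.** The dilution arithmetic is not open to dispute. The objection is to how much follows from it, and most of it stands.

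**Participant results.** A reader might infer that the three AChE endpoints are compromised. The documents do not support that. Each plate carries a five-level recombinant AChE standard in triplicate, and the data-analysis step converts absorbance to activity through a linear calibration curve. The spiked wells enter no participant calculation, so the error does not by itself bias any participant's AChE value.

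**Plate failure.** A reader might also infer that every plate would fail quality control. The appendix says only what treatment should produce. It gives no acceptance limit and no action if the limit is missed. Its label QC belongs to the separate 'Blood 2'/'Serum 2' samples, which are logged over time. Nor is the spiked control the only check on the plate; it is the only one described that contains an inhibitor.

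**Model dependence.** The near-zero residuals assume that 50 nM is the strength behind the 20-40% band and that inhibition has no floor. The appendix mentions butyrylcholinesterase as well as AChE activity in its sample types, so a floor cannot be ruled out from the text. If the laboratory prepared 50 µM and saw 20-40%, the fault is a unit slip and the control may be sound. Repeated use of nM points towards an omitted 1:1,000 step, but the documents cannot settle it.

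**Reach.** Protocol Section 9.19 sends pharmacodynamic measurements to an SOP not available here, and the appendix is marked V0.4. Nothing shows that plates were run with this recipe.

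None of this makes the written instruction correct.

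**Conclusion.** The recipe is wrong as written, on the protocol's own figures and without any assumption: 1,000-fold above the stated strength by the ratio, about 2,200-fold by the example, and the two disagree by a factor of 2.2. That the control would miss its 20-40% expectation is conditional on the assumed dose-response curve; it holds for Hill slopes of 1 and 0.5, with residual activity no higher than about 2%.

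The consequence is limited to the phenserine inhibition control for a set of descriptive secondary endpoints. The primary exosome endpoint and the sample size are untouched. Calling the AChE results unreliable, or asking for all samples to be re-assayed, would go beyond the documents. Severity: should-fix laboratory-appendix correction.

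**What to change.** 1. The laboratory confirms the intended concentration and reconciles the preparation step, the plate legend, assay step 2 and the expected-activity statement.
2. If 50 nM is intended, write an overall 1:200,000 serial dilution, for example 100 µl stock + 19.9 ml buffer = 50 µM, then 1:1,000 = 50 nM.
3. If 50 µM is intended, correct the unit wherever 50 nM appears, and correct the example to 19.9 ml of buffer (or 45 µl of stock in a total of 9.0 ml, since 9.0/200 = 0.045 ml).
4. State the in-well concentration: prepared strength × 0.88, so 44 nM for 50 nM buffer or 44 µM for 50 µM buffer. Verify the 20-40% band at that concentration in one run.
5. Check the control tracking sheet for plates made with the written recipe. Where there are any, repeat only the control verification.

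The cost is a text correction and one verification run, best done before AChE results are released.

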Phenserine showed high and predictable oral bioavailability across the dose levels. Over the 4-fold increase in dose, AUC₀₋₂₄ values increased by ~25%. T_{max} values ranged from 1.25-1.54 hr, and t_{1/2 elim} = 6.53 hr. Erythrocyte AChE inhibition reached peak values of 12%, 23% and 46% at 2 hours postdose for the 10, 15, and 20 mg/kg dose groups, respectively, and showed a linear relationship to phenserine plasma concentrations. Other studies have demonstrated that phenserine's effects on cognition and other neuropsychiatric assessments are positively correlated with increased CSF Aβ₄₀ and sAβPP levels as well as improved regional cerebral blood flow (rCBF) and metabolic rate for glucose (rCMRglc). In addition, CSF Aβ₄₂ levels, the Aβ₄₂/40 ratio, P-tau, and T-tau correlated negatively with rCMRglc and cognition (7,8).

In a follow-on study (5) elderly but otherwise healthy volunteers were randomized to receive once daily doses of phenserine immediate release capsules at 5 mg QD, 5 mg BID, 10 mg QD, or 10 mg BID (8 subjects/group) for 6 days. There were no dose-limiting or serious adverse events (AEs) reported for any subject. In addition, there were no clinically significant findings in clinical laboratory measures or ECG assessments across all dose groups. Peak plasma concentrations increased with dose but were similar across the QD and BID dosage regimens for each dose level. In addition, AUC₀₋₂₄ values remained consistent over the 6-day treatment period confirming that drug accumulation does not occur with repeated dosing. Erythrocyte AChE inhibition of 15% and 30% were observed for the 5 and 10 mg dose groups, respectively, regardless of the once- or twice-daily dosing schedules.

A subsequent NIA-sponsored Phase 2, 12-week RCT in 72 patients indicated that phenserine (10-15 mg b.i.d.) conferred significant improvements in cognitive function and a trend towards improvement in global outcome in people receiving the higher dose, with Cohen's D effect sizes of 0.3-0.4 for symptomatic benefits (6).

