2.3.4. Overall Benefit Risk Conclusion

Overall, there is strong pre-clinical evidence of phenserine's biological effects that are relevant to the treatment of AD and other neurodegenerative conditions, with a novel effect on apoptosis in addition to cholinesterase inhibition. Previous clinical trials with phenserine suggest a good clinical safety profile and offer some encouraging indications of potential benefit. The protocol has been designed based on the learnings of the failed Axonyx program and will ensure that the patient population is appropriate and that the study assessments more fully characterize phenserine's potential therapeutic utility across more robust measures of pharmacodynamic effects and any correlated improvements in cognitive function.

3. Objectives, and Endpoints

The study will be conducted as a 2 arm, parallel group, randomized RCT of phenserine compared to donepezil in people with early or mild AD. A total of 16 participants will be recruited from sites across Norway and be supported by the PROTECT platform. Eligible participants will be randomized 6:2 to phenserine or donepezil in an unblinded manner.

The end of the research active period for this study is set to January 1, 2028. All analyses within the scope of this study will be completed by this date.

The pharmacodynamic (PD), pharmacokinetic (PK), and safety data from this study are intended to inform dose selection and study design for a subsequent Phase 2 study of phenserine over a longer treatment duration in people with early to mild Alzheimer's disease (AD). The objectives of the study are as follows:

Primary Objective:

To assess the effects of phenserine compared to donepezil on exosome biomarkers of cell death in people with early or mild AD.

Key Secondary Objective:

To evaluate the safety and tolerability profile, of phenserine at ascending doses up to 10 mg tds as compared to donepezil at doses up to 10 mg od in participants with early or mild AD.

Other Secondary Objectives:

To evaluate steady state blood levels of phenserine for the purpose of characterizing and comparing dose-response relationships for pharmacodynamic outcomes and key safety assessments.

To evaluate the proportion of participants in the phenserine arm who achieve the target AChE inhibition of approximately 45%, stratified by dose regimen and the time required to reach the target AChE inhibition of ~45% and the duration participants maintain this inhibition during the treatment period.

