3.1. Table 2. Objectives and endpoints

Objectives	Endpoints
Primary	
To assess the effects of phenserine compared to donepezil on exosome biomarkers of cell death in people with early or mild AD.	Changes in endosomal biomarkers of pre-programmed cell death, synaptic integrity and function, neuroinflammation, and AD-related protein trafficking in participants treated with phenserine versus those treated with donepezil. Although patients and site staff will be unblinded to the treatment modality administered, they will be blinded to the results of the biomarker evaluations until the study is completed.
Secondary	
To evaluate the safety and tolerability profile of phenserine at ascending doses up to 10 mg tds as compared to donepezil at doses up to 10 mg od in participants with early or mild AD.	Safety and tolerability of phenserine compared to donepezil in participants with early or mild AD based on the frequencies of reported or observed adverse events (AEs) and serious adverse events (SAE), vital signs, clinical laboratory evaluations, ECGs, modified CSSRS scores.
Other secondary	
To evaluate steady state blood levels of phenserine and donepezil for the purpose of characterizing and comparing dose-response relationships for pharmacodynamic outcomes and key safety assessments.	Pharmacokinetic parameters will be assessed at steady state for determination of dose-response relationships for phenserine and donepezil
To evaluate the proportion of participants in the phenserine arm who achieve the target cholinesterase inhibition of approximately 45% across different dosing regimens, as well as the time required to reach the target and the duration of maintaining this inhibition.	Proportion of participants in the phenserine arm achieving the target cholinesterase inhibition of ~45%, stratified by dosing regimen and the time to reach the target inhibition and the duration of maintaining this target will be assessed and recorded
To evaluate compliance, the study will measure the extent to which participants	Compliance will be recorded, based on drug count and subject diary, including the proportion of

take the study medication according to the protocol. Compliance will be assessed using the subject diary and the registration of returned capsules.	participants complying with the treatment schedule. Compliance is defined as drug intake within 80-120% of the scheduled dosing.
Exploratory	

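### The assay in Protocol Appendix 10 has no step that separates AChE from BChE, and no blood matrix is named for the 45% AChE endpoint, so the reading can be biased in a direction and by an amount the documents do not fix

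*Protocol*

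**What the plan says.** **Endpoint.** Protocol 3 (Other Secondary Objectives) sets out to evaluate phenserine participants "who achieve the target AChE inhibition of approximately 45" per cent, together with time to target and duration at target. Table 2 (Protocol 3.1) words the same objective as "target cholinesterase inhibition of approximately 45% across different dosing regimens". SAP 8.3 summarises the proportion at or above 45%, the time to target and the duration above it. It names no matrix and gives no formula for percent inhibition.

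**Assay named for the endpoint.** Protocol 3 (Other Secondary Endpoints): "Blood samples will be analyzed for Acetylcholinesterase (AChE) activity using a modified Micro-Ellman method (22) normalized to recombinant AChE enzyme activity". Details are left to Appendix 10.

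**Appendix 10.**
- The substrate step adds 20 µl of "15mM ATCh solution to each well with multichannel electronic pipette". No other substrate appears, and no BChE inhibitor is listed in the reagent table, the reagent preparation or the procedure.
- "Serum (AchE) and plasma (BchE) are to be diluted" 1:50 to 1:100 in assay buffer.
- "Whole blood samples are to be diluted" 1:100.
- The plate layout defines one quality-control material for whole-blood AChE and another for serum AChE.
- The reagent table shows two buffers, one at pH 8.2 and one at pH 7.2.
- The control reads: "Phenserine treatment (50nM) of samples should result in an activity decrease to 20-40% of normal levels".

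**Prior evidence.** Protocol 2.3.1 relies on red-cell data: "Erythrocyte AChE inhibition of 15% and 30% were observed for the 5 and 10 mg dose groups, respectively".

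**The concern.** Serum and plasma are both cell-free and differ essentially in clotting factors. The same substrate, reagents and read cannot report AChE in one and BChE in the other. The plasma label itself accepts that this acetylthiocholine read picks up BChE, and nothing in the procedure removes that signal from serum or whole blood. Normalising to recombinant AChE sets the unit of activity; it does not subtract another enzyme's turnover. Serum also contains no red cells, so a serum value is not comparable with the erythrocyte inhibition cited in Protocol 2.3.1.

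Three uses of the measurement are at stake: the 45% endpoints, the AChE axis of the exposure–response plots (SAP 8.2), and the comparison of inhibition between phenserine and donepezil with its correlation to other outcomes (Protocol 9.19). The last matters because Protocol 2.1 includes donepezil to control for cholinesterase inhibition. If the two drugs differ in how far they inhibit BChE, a mixed reading does not show whether AChE inhibition was matched.

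**Working it through.** **1. The appendix's own concentrations.**
- Thiol reagent (DTNB): 10 mM × 750/(750 + 33,000) × 270/300 = 0.2 mM. This agrees with the stated final value.
- Acetylthiocholine: 15 mM × 20/300 = 1.0 mM. This agrees.
- Phenserine control: 10 mM ÷ 200 = 0.05 mM = 50 µM. The appendix says 50 nM, which is 1,000 times lower. Its worked example, 100 µl made up with 8.9 ml, is 0.1 in 9.0 ml, or 1:90, giving 10,000 µM ÷ 90 = 111 µM. Reaching 50 nM from 10 mM takes a 200,000-fold dilution. The stated ratio, the example and the stated concentration are mutually inconsistent.

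**2. What the reading contains.** Let f be the BChE share of the uninhibited signal, iA the AChE inhibition and iB the BChE inhibition. Then

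reading = (1−f)·iA + f·iB, and bias = reading − iA = f·(iB − iA).

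The reading is too low only if f > 0 and iB < iA. Neither document gives f for any matrix, or iB for either drug, so both are varied as assumptions.

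| True AChE inhibition 45% | f = 10% | f = 20% | f = 40% |
|---|---|---|---|
| iB = 0 | 40.5% | 36% | 27% |
| iB = 10% | 41.5% | 38% | 31% |
| iB = 45% | 45% | 45% | 45% |
| iB = 60% | 46.5% | 48% | 51% |

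Example: f = 20%, iB = 0 gives 0.8 × 45 = 36. With iB = 60% it gives 36 + 0.2 × 60 = 48.

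With iB = 0, the true inhibition needed to read 45% is 45/(1−f): 50%, 56% and 75% at the three values of f.

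**3. Effect on the count reaching target.** Inputs: n = 12 phenserine participants (Protocol 1.2). Assumptions: true inhibition normal with SD 10 percentage points, and iB = 0. Expected count = 12 × P(true inhibition ≥ 45/(1−f)).

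| Mean true inhibition | f = 0 | f = 20% | f = 40% |
|---|---|---|---|
| 50% (assumed) | 8.3 | 3.2 | 0.1 |
| 30% (Protocol 2.3.1, for a 10 mg dose) | 0.8 | about 0 | about 0 |

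For mean 50% and f = 20%: (56.25 − 50)/10 = 0.625, upper tail 0.266, and 12 × 0.266 = 3.2. On the 30% figure, few reach 45% even with a fully AChE-specific assay, so in that case the bias shows mainly in the continuous exposure–response data.

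**The case against.** The case on the other side has several parts.

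- **The measurand may be total cholinesterase.** The synopsis (Protocol 1.1), Table 2 and Protocol 6.3 speak of cholinesterase inhibition. If that is meant, a mixed signal is not a bias. But Protocol 3, SAP 4.5 and SAP 8.3 name AChE, so the wording has to be aligned in either case.
- **The matrix may be fixed elsewhere.** Appendix 10 points to a chapter on preanalytical handling that is not in the supplied text, and the cited method reference was not available. This stands as a limit: it is not shown that serum feeds the endpoint. Naming a matrix would still not add a BChE block to the listed reagents.
- **Less is open than it seems.** Whole blood is fixed at 1:100, the samples in the layout are at 1:100, and the alternative activity formula is restricted to pH 7.2. The dilution range concerns serum and plasma only. This stands.
- **Consequences are limited.** Escalation is decided on tolerability (Protocol 6.3 and 6.6) and SAP 8.3 is descriptive. This stands too.

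A reader might go further and infer that the endpoint is bound to understate AChE inhibition, or that a serum reading would fall close to zero. The documents support neither, because they give no selectivity for phenserine and no BChE share. A reader might also take the 20–40% residual activity in the control as the BChE share. It cannot serve: the residue could be incompletely inhibited AChE, and the control as written is not at the stated concentration.

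**Conclusion.** The concern holds in a conditional form. As written, Appendix 10 does not isolate AChE, gives serum and plasma incompatible enzyme labels under one procedure, and leaves the endpoint matrix unnamed in the supplied text. The bias is f·(iB − iA). It is downward if BChE contributes and is less inhibited than AChE: with iB = 0, a true 45% reads 40.5% to 27% for f between 10% and 40%. It is nil if the two are equally inhibited, and upward if BChE is inhibited more. Both f and iB are assumptions here.

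It would also go too far to say that the assay measures total blood cholinesterase. That describes whole blood; serum is a different, cell-free matrix, and the text does not say which is used. The damage is to secondary pharmacodynamic evidence passed to Phase 2, not to dose escalation. The 1,000-fold discrepancy in the phenserine control rests on no assumption.

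**What to change.** - **Matrix and labels.** In Protocol 3 and Appendix 10, name one matrix for the endpoint. Whole blood is the closest of those listed to the erythrocyte data cited in Protocol 2.3.1. Remove or correct the enzyme labels on serum and plasma, including the serum quality-control entry.
- **Specificity.** Add a BChE-selective inhibitor to the working solution, or run paired wells with and without it, after a bench check that it spares AChE.
- **Conditions.** State one buffer and one dilution for the endpoint assay.
- **Formula.** In SAP 8.3, define percent inhibition against the participant's own Day 0 value.
- **Wording.** Use AChE or cholinesterase consistently in Protocol 1.1, 3, 3.1 and 6.3.
- **Control.** Reconcile the stated 50 nM with the 1:200 ratio and the 1:90 worked example.

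The cost is one reagent, a short laboratory validation and text revisions. No visits are added, and no new samples are needed if whole blood is already being collected. If it is not, the sampling instructions must change as well.
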